6.2.2 Descriptive analyses

CRP and ferritin

Panels of individual spaghetti plots over time for CRP and ferritin will be provided using a logscale. The profiles of all participants in the respective treatment group will be included in these graphs as grey lines in the background and the respective individual participants profile will be plotted with darker color in the foreground. The respective applicable normal ranges will be added and it will be indicated by a symbol if a patient died.

Survival without the need for invasive mechanical ventilation

The numbers and percentages of responders will be calculated up to Day 15 and up to Day 29 respectively. It will be presented by treatment group together with the difference in response rates.

Improvement in clinical status

The numbers and percentages of responders will be calculated up to Day 15 and up to Day 29 respectively. It will be presented by treatment group together with the difference in response rates and a two-sided 90% CI based on Fishers exact test.

In addition a shift table of changes in response status will be provided with weekly time intervals (e.g. baseline, week 1, week 2, week 3 and week 4). For this the following response categories will be included:

- improvement of at least 1 step from baseline,
- no change from baseline
- worsening from baseline.

Also a stacked barchart illustrating the percentage of participants in each response categories as outlined above will be provided. Treatment groups will be presented next to each other. This will be provided for weeks 1, 2, 3 and 4.

For the subgroup analysis a shift table and stacked barchart for subgroup of participants with high baseline CRP by high and low corticosteroid dose during week 1 will be provided.

Clinical status over time

The 9-point ordinal scale will be summarized (mean, median, standard deviation, minimum, maximum, frequencies and percentages in each category) will be summarized by visit (including a time point for data from early discharge) and treatment group.

A stacked barchart illustrating the percentage of participants for each category of the 9-point ordinal scale with one bar will be provided. Treatment groups will be presented next to each other within one category. This will be provided for Day 8, Day 15, Day 21 and Day 29 (labeled as weeks 1, 2, 3 and 4).

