6.2.3 Statistical model, assumptions and hypotheses

CRP and ferritin

CRP levels are assumed to follow a log-normal distribution. Thus the log-transformed CRP data will be analyzed by fitting an MMRM model. Treatment, visit and their interaction as well as the three stratification factors will be included as fixed factors and baseline CRP as a covariate. Interactions between visit and each of the terms in the model will also be included. To model the dependency of observations an unstructured variance-covariance matrix will be fitted.

The analysis will be performed on the PD analysis set. The back-transformed geometric means for both treatment groups as well as the geometric mean ratios (MAS825 vs placebo) will be reported together with 90% confidence intervals (CIs) for each visit. The 1-sided p-value for the overall treatment factor will be reported. Ferritin levels will also be analyzed in the same manner.

For the subgroup analysis the same model as for the original MMRM analysis including in addition a factor for high vs. low corticosteroid use during week 1 (see [Section 7.2.2](#) for details) and its 3-way interaction with treatment and visit. The geometric means (+/-SE) per corticosteroid category and treatment group as well as the ratio of geometric mean (90% CI) per corticosteroid group are reported for each visit.

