7.2.2 Treatment

Concomitant medications and significant non-drug therapies prior to and after the start of the study treatment will be listed and summarized according to the Anatomical Therapeutic Chemical (ATC) classification system by treatment group. For corticosteroids ATC-Subclasses will be added. Convalescent plasma treatment will be included in the anti-viral treatment presentations.

For any of the below mentioned three treatment categories, if it started prior to treatment and continued during the study, it will be reported under baseline as well as part of SoC during study participation.

A graphical presentation of the cumulative use of different concomitant medications at baseline over the course of the study by treatment group will be provided. For this the cumulative average percentage use will be plotted on the y-axis over the cumulative number of enrolled participants on the x-axis. This presentation will be provided for the following medications:

- Dexamethasone
- Remdesivir
- Hydroxchloroquine or Chloroquine
- Anti-coagulants (using ATC class as provided)

Corticosteroids use

The number and percentage of patients will be summarized by treatment group for the following parameters:

- receiving any corticosteroids after randomization
- receiving Dexamethasone after randomization reporting the highest total daily dose observed during the study using the following ranges:
<6 mg, 6-<12 mg, >= 12 mg

The following presentations will be based on the prednisone equivalent dose (see Appendix for details):

- with a change in their corticosteroids dose after randomization (increased/reduced/stable dose)
- receiving corticosteroids after randomization reporting the highest total daily dose observed during the study using the following ranges:
<7.5 mg, 7.5-<20 mg, >= 20 mg

For subgroup analyses the participants with a high vs. a low corticosteroid dose during the first week following randomization were identified. This was defined as follows:

- Considering any corticosteroid mediation selected by ATC class administered between randomization and the following 7 days (i.e. start date < day 8 and end date > 0).
- Only medication reported with a unit of “mg” was included
- Doses are converted into prednisone equivalent doses applying [Table 10-2](#).
- The total daily dose is derived based in the administration frequency reported in the CRF:
 1. “ONCE”, “QD”, “QID”, “Q24H” – factor 1
 2. “BID” – factor 2
 3. “TID”, “Q8H” – factor 3

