 4. “Q6H” – factor 4
- The total dose administered during the first week is derived based on the actual number of days the drug was administered in this period. This is done on a “day” scale, i.e. additional details on administration times are not considered.
- The sum of the total daily doses during the first week in the study is calculated
- The average total daily dose is derived by dividing the sum of the total daily doses by 7.
- A dose of zero is added for any participants not receiving corticosteroids during the first week.
- The average daily prednisone equivalent doses during the first week (dailydose1wk) in mg are categorized as follows:
 - dailydose1wk = 0: “none”
 - dailydose1wk <= 10 (including zero): “<=10”
 - 10 < dailydose1wk <= 20: “>10-20”
 - 20 < dailydose1wk <= 50: “>20-50”
 - 50 < dailydose1wk <= 100: “>50-100”
 - 100 < dailydose1wk <= 200: “>100-200”
 - 200 < dailydose1wk: “>200”

A stacked barchart is provided showing the distribution in these dose categories by treatment group.

- For further subgroup analyses the categories “<=10 mg (Low)” and “>10 mg (High)” are used.

For the medications listed below barcharts on the “counts” use of corticosteroids at baseline by treatment group will be given.

- Dexamethasone
- Methylprednisolone
- Prednisone
- Other

- None

Anti-viral medication use

The number and percentage of patients will be summarized by treatment group for the following parameters:

- receiving any anti-viral medication after randomization
- receiving hydroxychloroquine/chloroquine/remdesivir/faripivavir/ritonavir/lopinavir/convalescent plasma after randomization receiving a combination of the above anti-viral medications after randomization tabulated by all combinations actually occurring.

For the medications listed below barcharts on the “counts” use of anti-virals at baseline by treatment group will be given.

- Azithromycin
- Hydroxychloroquine
- Remdesivir
- Convalescent plasma
- Immunoglobulin G human
- Other
- None

For convalescent plasma and immunoglobulin G human, also consider them as baseline records if any participant had them administered before screening/baseline visit.

Anti-coagulation therapy

The number and percentage of patients will be summarized by treatment group for the following parameters:

- receiving any anti-coagulation medication after randomization

The “counts” at baseline will be displayed in a barchart.

• Anti-infectives therapy

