7.2.3 Vital signs

Vital sign measurements include respiratory rate, pulse rate (PR), systolic and diastolic blood pressure, mean arterial pressure body temperature, weight and BMI. Peripheral oxygen saturation on room air should also be measured at the same time as the vitals. For participants requiring supplemental oxygen, the oxygen flow rate (L/min) and/or FiO₂ is also recorded.

Summary statistics will be provided by treatment group and visit/time.

The following exploratory MMRM analyses were conducted for body temperature:

1. Including all participants using the safety analysis set.
2. on the high baseline CRP subgroup and by corticosteroid dose during the first week following randomization using the “PD analysis set” is used.

In addition only participants in the high baseline CRP group are considered. The high baseline CRP group is defined as any subject with a baseline CRP value > median baseline CRP value of all participants in this study.

For analysis 1. the MMRM model is including treatment, visit and their interaction as well as the three stratification factors and their interaction with visit as fixed factors and baseline body temperature as a covariate. Interactions between visit and each of the terms in the model will also be included. To model the dependency of observations an unstructured variance-covariance matrix will be fitted.

The means per treatment group as well as the mean difference (MAS825 vs. Placebo) will be reported together with 90% confidence intervals (CIs) for each visit. In addition the 1-sided p-values for the overall treatment factor will be reported.

Estimated mean body temperatures +/- SE will be plotted over time by treatment group.

For analysis 2. the same model as for the original MMRM analysis including in addition a factor for high vs. low corticosteroid use during week 1 (see [Section 7.2.2](#) for details) and its 3-way interaction with treatment and visit.

The means (+/-SE) per corticosteroid category and treatment group as well as the mean differences (90% CI) per corticosteroid group are reported for each visit.

A line plot of the means (+/-SE) are provided by corticosteroid dose category and treatment group together with the estimated values of the primary analyses by treatment group over time. Side-by-side a second line plot on the treatment differences (90% CI) per by corticosteroid dose category together with the estimated treatment difference (90% CI) of the primary analyses over time is given.

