10.7 Steroid conversion factors

Steroids will be displayed using prednisone equivalent doses. The doses displayed in the following table are considered equivalent. To determine prednisone equivalent doses, doses (in unit mg) will be multiplied by the conversion factor shown in [Table 10-2](#). In case multiple corticosteroids are used at a certain visit the prednisone equivalent doses will be added up to obtain the total prednisone equivalent dose.

Table 10-2 Steroids conversion factors

WHO drug code	Preferred Term Corticosteroid	Equivalent Dose [mg]	Conversion Factor
000447xx	Prednisone	5	1
000162xx	Prednisolone	5	1
000496xx	Methylprednisolone	4	1.25
012428xx	Meprednisone	4	1.25
001867xx	Prednylidene	5 5/7	0.875
000319xx	Triamcinolone	4	1.25
000146xx	Cortisone	25	0.2
000286xx	Hydrocortisone	20	0.25
002131xx	Fludrocortisone	2	2.5
000085xx	Betamethasone	0.75	20/3
000664xx	Paramethasone	2	2.5
000160xx	Dexamethasone	0.75	20/3
008827xx	Deflazacort	6	5/6

Commercially Confidential Information

Commercially Confidential Information

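### The SAP's steroid derivation counts QID as one administration a day, which understates QID-coded doses four-fold in the week-1 dose chart and the High/Low steroid subgroup

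*SAP*

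**What the plan says.** SAP 7.2.2 (Corticosteroids use) derives a week-1 average daily steroid dose in four steps.

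- Each dose in mg is converted to prednisone equivalents with Table 10-2.
- It is multiplied by a factor for the CRF frequency code: "ONCE”, “QD”, “QID”, “Q24H” – factor 1", then BID at 2, "TID”, “Q8H” – factor 3", and Q6H at 4.
- Daily totals are summed over the days on which the drug was given in the first week.
- "The average total daily dose is derived by dividing the sum of the total daily doses by 7".

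The average is placed in dose categories with cut-points at 10, 20, 50, 100 and 200 mg, shown as a stacked bar chart by treatment group. It is also dichotomised: "For further subgroup analyses the categories “<=10 mg (Low)” and “>10 mg (High)” are used".

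The dichotomy is used in three places:

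- SAP 6.2.2, shift tables and bar charts of clinical status for the "subgroup of participants with high baseline CRP by high and low corticosteroid dose during week 1";
- SAP 6.2.3, the CRP and ferritin subgroup MMRM, "including in addition a factor for high vs. low corticosteroid use during week 1", with its three-way interaction with treatment and visit;
- SAP 7.2.3, the second body-temperature MMRM, "on the high baseline CRP subgroup and by corticosteroid dose during the first week following randomization".

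Neither document defines QID or gives another rule for it.

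**The concern.** In ordinary prescribing notation QID is four times a day. The SAP groups it with the once-daily codes, yet gives the equivalent interval code, Q6H, factor 4. The list already pairs TID with Q8H at 3, so the same logic pairs QID with Q6H. As written, a QID record yields a smaller daily dose than a BID or TID record of the same strength.

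The subgroup outputs are there to show whether background steroid changes the apparent effect of MAS825 on CRP, ferritin, clinical status and temperature. Moving truly high-dose participants into Low could blur that contrast. The groups are also small. About 120 participants are planned. The clinical-status and temperature subgroups keep only those with baseline CRP above the median, so at most about 60. Two arms by two steroid levels then gives at most about 60 / 4 = 15 per cell on average, and a few misclassified participants could alter a cell.

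There is a secondary caveat. High and Low are defined by steroid given in the week after randomisation, so treatment contrasts within either level are not randomised comparisons. They may be biased in principle; the size is unknown.

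**Working it through.** **1. Multipliers against administrations per day** (QxH = 24/x; QID at its standard meaning)

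| Code | SAP factor | Administrations per day | Agrees |
|---|---|---|---|
| ONCE, QD, Q24H | 1 | 1 | yes |
| BID | 2 | 2 | yes |
| TID, Q8H | 3 | 3 | yes |
| Q6H | 4 | 4 | yes |
| QID | 1 | 4 | **no** |

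Seven of the eight codes reproduce; only QID does not.

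**2. Formula.** Week-1 average = dose per administration × Table 10-2 factor × frequency multiplier × days given / 7.

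**3. Same dose, different code** (illustrative regimen, not from the documents). Hydrocortisone 50 mg × 0.25 = 12.5 mg prednisone-equivalent per administration. Over 7 days:

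- BID: 12.5 × 2 = 25.0 mg/day
- TID: 12.5 × 3 = 37.5 mg/day
- Q6H: 12.5 × 4 = 50.0 mg/day
- QID as written: 12.5 × 1 = 12.5 mg/day

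**4. High/Low label when all week-1 steroid is QID-coded.** With D the true average, the SAP computes D/4. The label is wrong when D > 10 and D/4 ≤ 10, that is, for D above 10 and up to 40 mg/day. Illustrations with assumed doses:

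| Regimen coded QID | SAP (factor 1) | Factor 4 | Label: SAP / factor 4 |
|---|---|---|---|
| Hydrocortisone 50 mg, 5 days | 12.5 × 5/7 = 8.93 | 35.71 | Low / High |
| Hydrocortisone 50 mg, 6 days | 12.5 × 6/7 = 10.71 | 42.86 | High / High |
| Methylprednisolone 40 mg, 1 day | 50 × 1/7 = 7.14 | 28.57 | Low / High |
| Methylprednisolone 40 mg, 2 days | 50 × 2/7 = 14.29 | 57.14 | High / High |
| Prednisone 10 mg, 7 days | 10 × 7/7 = 10.0 | 40.0 | Low / High |

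**5. Dose-category chart, all steroid QID-coded**

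| True average D (mg/day) | Correct category | Category shown |
|---|---|---|
| up to 10 | ≤10 | ≤10 (correct) |
| >10 to 20 | >10–20 | ≤10 |
| >20 to 40 | >20–50 | ≤10 |
| >40 to 50 | >20–50 | >10–20 |
| >50 to 80 | >50–100 | >10–20 |
| >80 to 100 | >50–100 | >20–50 |
| >100 to 200 | >100–200 | >20–50 |
| >200 to 400 | >200 | >50–100 |
| >400 to 800 | >200 | >100–200 |
| above 800 | >200 | >200 (correct) |

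**6. Mixed records.** Let q be the true QID-coded average and o the average from all other steroid. The label changes only if q + o > 10 and q/4 + o ≤ 10. In the 5-day hydrocortisone example, o may be at most 10 − 8.93 = 1.07 mg/day. A single once-daily dose of dexamethasone 6 mg adds 6 × 20/3 / 7 = 5.71, giving 8.93 + 5.71 = 14.64, so the participant stays High.

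**The case against.** Several points on the other side are fair.

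- **The window for a wrong label is narrow.** For a QID-only participant it needs prednisone-equivalent per administration × days of more than 17.5 mg (so that 4 × that / 7 exceeds 10) and at most 70 mg (so that that / 7 does not). The 5-day hydrocortisone course flips, but the same course for 6 or 7 days (10.71 and 12.5) is still High under the SAP rule. Methylprednisolone 40 mg QID for 2 days (14.29) and dexamethasone 6 mg QID for 2 days (40 × 2/7 = 11.43) are also still High. This stands: wrong labels come from short courses or small doses per administration. The wider range of up to 800 mg/day concerns the bar chart only, and no document shows doses near its upper end.
- **The number of QID records is not given.** It may be very small. This stands: the documents support saying the results could be blurred, not that they are.
- **The CRF is not visible, so QID might have been used for once daily.** That is possible, but nothing says so and the rest of the list points the other way. The fix allows for it.
- **The subgroup outputs are already descriptive or exploratory.** Largely true. The clinical-status displays sit under descriptive analyses, SAP 7.2.3 calls its models exploratory, and no p-value or success criterion is stated for the subgroup models. The CRP/ferritin subgroup model in 6.2.3 carries no such label, so the caveat still has some use, but it is secondary to the coding error.

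None of this makes factor 1 right for a four-times-daily code.

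**Conclusion.** The derivation is wrong as written, provided QID has its standard meaning. Each QID-coded record is understated four-fold; a participant who also has other steroid records is understated by less overall. With QID-only steroid, High becomes Low for true averages above 10 and up to 40 mg/day, and the chart category is too low above 10 and up to 800 mg/day.

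The damage is limited to the week-1 dose chart and the subgroup outputs in SAP 6.2.2, 6.2.3 and 7.2.3. The primary ANCOVA (6.1.3), its sensitivity analysis (6.1.4) and the main CRP/ferritin MMRM (6.2.3) do not use this variable. Confidence in the inconsistency is high; its realised effect cannot be computed from the documents. It should be fixed, because it is unambiguous and cheap to correct, but it does not threaten the trial's main conclusion.

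**What to change.** 1. In SAP 7.2.2, move QID to factor 4 beside Q6H. If the CRF code means something else, state that meaning in the SAP. Then re-derive the week-1 dose categories and the High/Low groups and re-run the chart and subgroup outputs. The cost is one code moved, or one sentence added, and a re-run.

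2. State that treatment contrasts within High or Low are descriptive because the split uses post-randomisation steroid. This is needed mainly for the CRP/ferritin subgroup model and has no analysis cost.

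A split on prednisone-equivalent daily dose at randomisation is optional. It would need the corrected frequency factors applied to baseline records: SAP 10.7 covers conversion and says that "the prednisone equivalent doses will be added up to obtain the total prednisone equivalent dose", but neither it nor 7.2.1 gives a frequency rule. It could produce less even groups and would not describe steroid started after randomisation.

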7.2.3 Vital signs

Vital sign measurements include respiratory rate, pulse rate (PR), systolic and diastolic blood pressure, mean arterial pressure body temperature, weight and BMI. Peripheral oxygen saturation on room air should also be measured at the same time as the vitals. For participants requiring supplemental oxygen, the oxygen flow rate (L/min) and/or FiO₂ is also recorded.

Summary statistics will be provided by treatment group and visit/time.

The following exploratory MMRM analyses were conducted for body temperature:

1. Including all participants using the safety analysis set.
2. on the high baseline CRP subgroup and by corticosteroid dose during the first week following randomization using the “PD analysis set” is used.

In addition only participants in the high baseline CRP group are considered. The high baseline CRP group is defined as any subject with a baseline CRP value > median baseline CRP value of all participants in this study.

For analysis 1. the MMRM model is including treatment, visit and their interaction as well as the three stratification factors and their interaction with visit as fixed factors and baseline body temperature as a covariate. Interactions between visit and each of the terms in the model will also be included. To model the dependency of observations an unstructured variance-covariance matrix will be fitted.

The means per treatment group as well as the mean difference (MAS825 vs. Placebo) will be reported together with 90% confidence intervals (CIs) for each visit. In addition the 1-sided p-values for the overall treatment factor will be reported.

Estimated mean body temperatures +/- SE will be plotted over time by treatment group.

For analysis 2. the same model as for the original MMRM analysis including in addition a factor for high vs. low corticosteroid use during week 1 (see [Section 7.2.2](#) for details) and its 3-way interaction with treatment and visit.

The means (+/-SE) per corticosteroid category and treatment group as well as the mean differences (90% CI) per corticosteroid group are reported for each visit.

A line plot of the means (+/-SE) are provided by corticosteroid dose category and treatment group together with the estimated values of the primary analyses by treatment group over time. Side-by-side a second line plot on the treatment differences (90% CI) per by corticosteroid dose category together with the estimated treatment difference (90% CI) of the primary analyses over time is given.

7.2.4 ECG evaluations

Heart rate, PR, QRS, QT, QTcF, and RR intervals will be obtained from ECGs (12-lead or 5-lead) for each participant during the study. ECG data will be read and interpreted locally.

Categorical analysis of QT/QTcF interval data based on the number of participants meeting or exceeding predefined limits in terms of absolute QT/QTcF intervals or changes from baseline will be presented.

Summary statistics will be provided by treatment group and visit/time.

7.2.5 Clinical laboratory evaluations

Summary statistics will be provided by treatment group and visit/time.

In case for one parameter multiple types of assessments were reported for the same visit/assessment the following rules are applied for any analysis e.g. summarizing the results:

- In case both absolute counts and percentages (e.g. “bands” or ratios) are provided, absolute counts are used.
- In case both Urea and BUN parameters are provided, Urea is used.
- In case for troponin multiple versions are provided (e.g. troponin T, I and/or C), troponin T is used; if not available troponin I is used.

In addition to the parameters collected the ratio of Urea/creatinine will be reported, where both parameters are converted to the same unit e.g. mg/dL (see [Section 10.3](#) for conversion details for Urea).

Estimated mean values +/- SE will be plotted over time by treatment group for each of the following lab parameters.

- Leukocytes, Neutrophils, Eosinophils, and Platelets.

To ensure that lab parameters only have numerical values, censored values will be imputed as follows

- Values like <xx.x are replaced by xx.x/2.
- Values like >xx.x are replaced by xx.x.

